3.11 Analysis of Safety Outcomes

3.11.1 Adverse Events of Special Interest

3.11.1.1 Definitions & Derivations

An Adverse Event (AE) is any undesirable medical event occurring to a subject in a clinical trial, whether or not related to the trial medications.

Drug-related AEs are AEs with a causality to drug being possibly, probably, definitely related or with a missing causality.

The only non-serious Adverse Events to be recorded are Adverse Events of Special Interest (AESIs). An AESI is the subset of AEs that are due to:

- Dizziness or any other symptom or event possibly related to hypotension,
- Abnormality detected in laboratory assessments of sodium, potassium, uric acid, glucose, lipids, creatinine or eGFR,
- Symptom of pedal edema reported by the participant,
- Any other symptom or laboratory abnormality that led to treatment withdrawal.

AESI include events occurring during Run-in, Randomization Period, and Follow-up.

A Serious Adverse Event (SAE) is any AE that meets one or more of the following criteria:

- Results in death;
- Is life-threatening;
- Requires in-patient hospitalization or prolongation of existing hospitalization;
- Results in persistent or significant disability/incapacity;
- Results in a congenital anomaly/birth defect.

Important medical events that may not result in death, be life-threatening, or require hospitalization may be considered serious when, based upon appropriate medical judgment, they may jeopardize the patient or subject and may require medical or surgical intervention to prevent one of the outcomes listed in this definition.

AESIs and SAEs will be recorded from time of informed consent up to 30 days after trial medication discontinuation.

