17.1.2. Adverse Event of Special Interest

The following AEs are considered AESIs and will be collected:

- Symptomatic hypotension: Dizziness or any other symptom or event possibly related to hypotension
- Abnormal laboratory findings of sodium, potassium, uric acid, glucose, lipids, creatinine or eGFR
- Headache
- Peripheral edema
- Any other symptom or laboratory abnormality that led to permanent discontinuation of trial medication.

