1 ADMINISTRATIVE INFORMATION

1.1 Trial Identifiers

• Protocol Number: GMRx2-HTN-2020-ACT1, Version 6.0, Date 10 October 2023

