2.4.2.2 Secondary

- Percentage of participants discontinued trial medication due to AE/SAE from randomization to follow-up Week 6.
- Percentage of participants with an SAE from randomization to follow-up Week 12.
- Percentage of participants with an SAE from randomization to follow-up Week 6.

- Percentage of participants with symptomatic hypotension from randomization to follow-up Week 12.
- Percentage of participants with symptomatic hypotension from randomization to follow-up Week 6.
- Percentage of participants with serum sodium concentration below 135 mmol/l at follow-up Week 12.
- Percentage of participants with serum sodium concentration below 135 mmol/l at follow-up Week 6.
- Percentage of participants with serum sodium concentration above 145 mmol/l at follow-up Week 12.
- Percentage of participants with serum sodium concentration above 145 mmol/l at follow-up Week 6.
- Percentage of participants with serum potassium concentration below 3.5 mmol/l at follow-up Week 12.
- Percentage of participants with serum potassium concentration below 3.5 mmol/l at follow-up Week 6.
- Percentage of participants with serum potassium concentration above 5.5 mmol/l at follow-up Week 12.
- Percentage of participants with serum potassium concentration above 5.5 mmol/l at follow-up Week 6.
- Percentage of participants with serum sodium <135mmol/l or >145 mmol/l, and/or serum potassium <3.5 mmol/l or >5.5mmol/l at follow-up Week 12.
- Percentage of participants with serum sodium <135mmol/l or >145 mmol/l, and/or serum potassium <3.5 mmol/l or >5.5mmol/l at follow-up Week 6.
- Percentage of participants with eGFR drop of over 30% from randomization to follow-up Week 12.
- Percentage of participants with eGFR drop of over 30% from randomization to follow-up Week 6.
- Percentage of participants with orthostatic hypotension at Week 6,
- Percentage of participants with orthostatic hypotension at Week 12
- Percentage of participants with orthostatic hypertension at Week 6,
- Percentage of participants with orthostatic hypertension at Week 12

In addition, descriptive safety data will be reported on:

- Percentage of participants discontinued trial medication due to AE/SAE during the active run-in period.
- All SAEs, by severity and by System Organ Class (SOC) criteria in the run-in period and by trial medication group in the randomized period and safety follow-up period.

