Mixed models with repeated measures (MMRM) will be applied for continuous endpoints using the same approach as the primary endpoint (with no imputations applied). Results will be presented in a similar fashion as home BP. Standing clinic BP measurements will be summarised descriptively by visit. Complete case analysis will be performed with no imputations for continuous endpoints.

Binary secondary endpoints will be analyzed using GEE regression methods in the same manner as home BP endpoints. Risk differences and 95% confidence intervals will be computed for comparisons between GMRx2 and dual control treatments. Missing values at Week 6 and Week 12 will be imputed as "failures" for the analysis.

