3.11.1.2 Adverse Event Summaries

For the summary of safety parameters, AEs will be classified according to the treatment period and treatment received as of the start date of the AE (Section 3.5.3). If an AE is ongoing at the time of randomization, it will be allocated to the Period 1 treatment. If a treatment ongoing at randomization worsens following randomization, the AE worsening will be allocated to the Period 2 treatment.

AESIs and SAEs will be classified according to the MedDRA (Medical Dictionary for Regulatory Activities) system (version 24.0, March 2021) and summarized by system organ class and preferred term.

Treatment periods for AE summary include: Period 1, Period 2, Period 3, Randomization Period, and Period 4. The total number of events and incidence of participants experiencing AESIs will be tabulated by treatment group and overall for the specified study periods.

For each period, any AESI or SAEs that emerges or worsens during the period of interest will be summarized:

- Adverse Events of Special Interest,
- Serious AE,
- Related AESIs defined as those judged by the investigator to be 'possibly', 'probably' or 'definitely' related
- Related SAEs defined as those judged by the investigator to be 'possibly', 'probably' or 'definitely' related,
- AE leading to trial medication discontinuation
- AE leading to trial discontinuation defined as a request by the participant to withdraw from future follow-up visits

AESIs of abnormality detected in laboratory assessments for Period 1 will only include those whose lab value for that parameter was in the normal range at baseline. Summaries of AESI and SAEs occurring during the Randomized Period will include risk differences with 95% CI, computed using the Newcombe hybrid score method (with continuity correction; https://pubmed.ncbi.nlm.nih.gov/21996567/), to evaluate GMRx2 against each dual control treatment group and overall. System organ classes and preferred terms with events occurring in at least 1% of the sample will be included.

In addition, the frequency and percentage of participants discontinuing treatment due to an AE will be reported with risk differences between treatment groups computed using the Newcombe hybrid score method (with continuity correction) to evaluate the primary safety endpoint among GMRx2 treatment participants compared to each dual control treatment group, and overall.

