Supply chain and logistics issues, substantial recruitment delays related to the COVID-19 pandemic and other unanticipated issues caused unplanned and significant trial conduct interruptions. As a result of these delays, a re-supply of IMP became infeasible. In addition, there had been independent review of study power at two Steering Committee meetings (6 Dec 2022 and 14 Feb 2023), based on the prespecified statistical approach of a mixed model repeated measures and blinded standard deviation of the overall sample, that the trial likely would have more statistical power than the univariate approach on which initial powering was modelled, as detailed above. These estimates were made without any reference to unblinded data. The Sponsor informed the Steering Committee of the pending IMP supply situation at their meeting on 11 April 2023, and given these challenges and blinded study power assessment that indicated the trial already had as much power as originally planned, the Steering Committees, the Steering Committee Chair wrote to the Sponsor on 21 April 2023 recommending a premature termination of recruitment. Based on the foregoing, the Company decided to terminate recruitment to the study. The final number of patients randomized was over 90% of the planned sample size.

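### The SAP's list of adverse events of special interest (AESIs) omits headache, which the protocol names, and its missing-as-failure rule has no clear meaning for the orthostatic safety endpoints

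*SAP*

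**What the plan says.** **AESI list.** Protocol 17.1.2 opens its list with "The following AEs are considered AESIs and will be collected". The five items are symptomatic hypotension, specified laboratory abnormalities, headache, peripheral edema, and any other symptom or laboratory abnormality leading to permanent discontinuation. SAP 3.11.1.1 says "The only non-serious Adverse Events to be recorded are Adverse Events of Special Interest (AESIs") and gives four items. Headache is absent, and edema appears as "Symptom of pedal edema reported by the participant". SAP 1.1 identifies its basis as "Protocol Number: GMRx2-HTN-2020-ACT1, Version 6.0, Date 10 October 2023", so both lists belong to the same protocol version. SAP 3.11.1.2 builds its AESI tables and Newcombe risk differences on this category, with the display rule "System organ classes and preferred terms with events occurring in at least 1% of the sample will be included".

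**Orthostatic endpoints.** Protocol 9.2.2 and SAP 2.4.2.2 class these as secondary safety outcomes. The SAP entries begin with "Percentage of participants with orthostatic hypotension at Week 6", and there are four in all (hypotension and hypertension, Weeks 6 and 12). SAP 3.10.3.2, which sits under secondary efficacy outcomes, lists them again with the clinic blood pressure endpoints. It sends the binary endpoints to GEE and says "Missing values at Week 6 and Week 12 will be imputed as" failures. The same section also plans complete-case proportions, risk differences, risk ratios and missing counts.

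**Recording end date.** Protocol 17.2.1 ends AESI and SAE collection at the Week 16 visit. Protocol 17.2.3 gives 30 days after discontinuation of medication for SAEs. SAP 3.11.1.1 gives 30 days for both.

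**The concern.** A SAP definition is what programmers implement. If the four-item list is used, part of an event type that the protocol singled out for collection disappears from the comparative safety tables, and SAP 2.6.2 records no decision to narrow the category.

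The missing-data rule was written for blood pressure control, where coding a missing value as not controlled is conservative. For a harm the direction is not defined. One reading hides events and the other creates them. When missingness differs between arms, either reading produces a between-group difference that comes from missing visits rather than from treatment.

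The analysis set for these endpoints is also in conflict, so two teams following the same SAP could report different modelled results.

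**Working it through.** The plan states no figure on this point, so there is none to reproduce. The check is a comparison of passages plus illustrative arithmetic.

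**1. Headache.** Under the SAP list, a non-serious headache can enter only as a symptom possibly related to hypotension or as a symptom that led to treatment withdrawal. The protocol has equivalents of both items and still names headache separately, so they are not a substitute. Every other non-serious headache falls outside the SAP definition.

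The documents give no headache rate. The only available scale is the display rule. SAP Appendix 2 says "The final number of patients randomized was over 90% of the planned sample size", and SAP 2.6.1 says recruitment stopped before 1500, so more than 0.90 × 1500 = 1350 and fewer than 1500 were randomized. If the sample means all randomized (assumed), 1% is 0.01 × 1351 = 13.5 to 0.01 × 1499 = 15.0, that is, 14 to 15 participants. This is the count at which headache would earn its own row, not an effect size. Headaches outside the SAP list would not count towards it.

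**2. Orthostatic endpoints: meaning of failure.** The only written meaning is in the Secondary Estimands part of SAP 3.10.1.1, where failure is non-achievement of the endpoint. The variables there are the efficacy list of SAP 2.4.1.2. Let p be the true event rate and m the proportion missing, with missingness unrelated to the event. The values of p and m are assumed.

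- Failure = endpoint not achieved (no event): modelled rate = (1 − m)p
- Failure = unfavourable outcome (event): modelled rate = (1 − m)p + m

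For p = 5%:

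| Missing | Coded as no event | Coded as event |
|---|---|---|
| 3% | 4.85% | 7.85% |
| 5% | 0.95 × 0.05 = 4.75% | 4.75% + 5% = 9.75% |
| 10% | 4.5% | 14.5% |

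With p = 5% in both arms, 8% missing on GMRx2 and 4% on a dual (true difference zero):

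- No-event coding: 0.92 × 0.05 − 0.96 × 0.05 = 4.6% − 4.8% = −0.2 points
- Event coding: (4.6% + 8%) − (4.8% + 4%) = 12.6% − 8.8% = +3.8 points

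Over true rates of 2% to 10% with the same missingness, the spurious differences are −0.1 to −0.4 and +3.9 to +3.6 points. Swapping the arms reverses the signs. The expected complete-case difference is zero when missingness is unrelated to the event.

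**3. Orthostatic endpoints: analysis set.** SAP 3.10.3.2 says the clinic binary endpoints follow the home method, and SAP 3.10.3.1 runs that GEE on the Randomized Set. Protocol 12.4 agrees, since it plans intention-to-treat throughout and GEE for binary safety outcomes. Against this, SAP 3.4.2 analyses safety endpoints by treatment received. SAP 3.11.2 puts binary secondary safety endpoints on randomized Safety Set participants, as treated. That sentence sits in the laboratory section and may be limited to it, but SAP 3.4.2 is not so limited.

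**4. Recording end date.** Medication stopped on day 84: 84 + 30 = day 114, against day 112 for Week 16, a nominal gap of 2 days. Stop on day 14: 112 − 44 = 68 days short of Week 16. Stop on day 42: 112 − 72 = 40 days short. Protocol 8.8 keeps early stoppers in follow-up to Week 16.

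**The case against.** The strongest reply is that the practical harm is small. Headache is collected under the protocol, SAP 3.11.1.2 tabulates AESIs by preferred term, and no passage says recorded AESIs are to be filtered against the SAP list. That stands to this extent: the loss occurs only if the list is applied as the definition. But avoiding it means departing from the SAP's written definition, which is a reason to correct the text. A reader might infer that headache data are not collected at all. Protocol 17.1.2 rules that out.

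On the orthostatic endpoints, SAP 3.10.3.2 already plans unimputed rates, contrasts and missing counts, and SAP 2.6.2 discloses multiple populations and expanded secondary safety methods. This also stands, and it confines the problem to the modelled result for 4 of the 21 secondary safety outcomes. It does not say which of two differing results is the reported one. Use of GEE is not itself an error, because Protocol 12.4 plans it.

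Two further inferences are tempting. One is that the GEE rates are biased downward. The documents do not establish this, because failure is defined only for efficacy endpoints and could equally be read as an event. The other is that no passage assigns an analysis set. SAP 3.10.3.1 and 3.10.3.2 together assign the Randomized Set. The defect is that this conflicts with the as-treated safety rules.

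**Conclusion.** The point holds as a correction that should be made, not as a threat to the trial's main conclusions. The AESI mismatch is certain from the text. Its effect is unquantified and depends on the SAP list being applied as the definition. The orthostatic rule as written is ambiguous for a harm. Under the assumed inputs and missingness unrelated to the event, the modelled rate is off by a fraction of a point under one reading and by several points under the other, while the planned complete-case results are untouched by the rule. The analysis-set conflict is real.

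The end-date difference is a minor consistency note. A reader might infer that events in early stoppers are dropped from the analysis. No passage excludes recorded events, and SAP 3.5.3 and 3.11.1.2 assign them by visit-defined period, so no analytic effect is shown. For SAEs the tension already exists within the protocol. Primary efficacy and primary safety outcomes are not affected.

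**What to change.** 1. Replace the four-item list in SAP 3.11.1.1 with the five items of Protocol 17.1.2.
2. State in SAP 3.10.3.2 that failure imputation does not apply to the orthostatic endpoints. Run their GEE on observed values beside the missing counts already planned, and state the assumption this makes about missingness.
3. Reconcile Protocol 12.4 and SAP 3.10.3.1 with SAP 3.4.2 and 3.11.2, and name one analysis set for the reported orthostatic result. If as-treated is chosen, note the departure from Protocol 12.4 in SAP 2.6.2.
4. Minor: reconcile the recording end date across Protocol 17.2.1, Protocol 17.2.3 and SAP 3.11.1.1, and say that all recorded events count in the visit-defined periods of SAP 3.5.3.

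The cost is SAP text, one protocol clarification for the end date, and a changed input to the orthostatic GEE, plus its grouping if as-treated is chosen. No new visits or data are needed, and sample size, power and alpha do not change.

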3.11.1.2 Adverse Event Summaries

For the summary of safety parameters, AEs will be classified according to the treatment period and treatment received as of the start date of the AE (Section 3.5.3). If an AE is ongoing at the time of randomization, it will be allocated to the Period 1 treatment. If a treatment ongoing at randomization worsens following randomization, the AE worsening will be allocated to the Period 2 treatment.

AESIs and SAEs will be classified according to the MedDRA (Medical Dictionary for Regulatory Activities) system (version 24.0, March 2021) and summarized by system organ class and preferred term.

Treatment periods for AE summary include: Period 1, Period 2, Period 3, Randomization Period, and Period 4. The total number of events and incidence of participants experiencing AESIs will be tabulated by treatment group and overall for the specified study periods.

For each period, any AESI or SAEs that emerges or worsens during the period of interest will be summarized:

- Adverse Events of Special Interest,
- Serious AE,
- Related AESIs defined as those judged by the investigator to be 'possibly', 'probably' or 'definitely' related
- Related SAEs defined as those judged by the investigator to be 'possibly', 'probably' or 'definitely' related,
- AE leading to trial medication discontinuation
- AE leading to trial discontinuation defined as a request by the participant to withdraw from future follow-up visits

AESIs of abnormality detected in laboratory assessments for Period 1 will only include those whose lab value for that parameter was in the normal range at baseline. Summaries of AESI and SAEs occurring during the Randomized Period will include risk differences with 95% CI, computed using the Newcombe hybrid score method (with continuity correction; https://pubmed.ncbi.nlm.nih.gov/21996567/), to evaluate GMRx2 against each dual control treatment group and overall. System organ classes and preferred terms with events occurring in at least 1% of the sample will be included.

In addition, the frequency and percentage of participants discontinuing treatment due to an AE will be reported with risk differences between treatment groups computed using the Newcombe hybrid score method (with continuity correction) to evaluate the primary safety endpoint among GMRx2 treatment participants compared to each dual control treatment group, and overall.

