8.2.1. Inclusion Criteria

At screening visit

1. Provided signed consent to participate in the trial.
2. Adult of age ≥ 18 years.
3. Clinic attended automated seated mean SBP (average of 3 measurements):
 - a. 140-179 mmHg on 0 BP-lowering drugs, or
 - b. 130-170 mmHg on 1 BP-lowering drug, or
 - c. 120-160 mmHg on 2 BP-lowering drugs, or
 - d. 110-150 mmHg on 3 BP-lowering drugs.

Note: A single tablet containing 2 or 3 different BP lowering agents (i.e. a combination medication) is considered as 2 or 3 BP lowering drugs, respectively.

At randomization visit

1. Home seated mean SBP 110-154 mmHg in the week prior to the randomization visit.
2. Adherence of 80-120% to run-in medication.
3. Tolerated run-in medication.
4. Adherence to home BP monitoring schedule: in the week before randomization, at least 6 measures (e.g. ≥ 2 sets of triplicate measures, ≥ 3 sets of duplicate measures) including at least 1 morning and 1 evening each with ≥ 2 measures
5. Morning is defined as any measure in the am and evening as any measure in the pm. Morning and evening do not have to be same day.

1.

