8.4. Intervention

8.4.1. Single-Blind Active Run-In Period

During the screening visit, enrolled participants will be asked to discontinue all current BP-lowering drug(s) if applicable and enter a single-blind active run-in period for 4 weeks with GMRx2 dose version 2. Participants will be advised to take the run-in capsule once daily in the morning at approximately the same time each day. For days on which BP is being measured, the run-in capsule should be taken directly after the morning home BP measurement.

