17.2.3. Reporting of AESIs & SAEs

At each trial scheduled visit and unscheduled visits during the trial, site staff will ask participants about the incidence of any AESIs or SAEs since the previous visit. Other AEs will not be recorded since these drugs are well-known and established with widespread use. Site staff may also become aware of the incidence of AEs during a phone call with participants. All SAEs that site staff becomes aware of from the time informed consent is obtained until 30 days after discontinuation of the trial medication must be recorded. The following information will be collected for each AESI and SAE: event name, date of onset, severity, a possible cause of the event, relationship to trial medication, action taken regarding the trial medication, treatment given to manage the event (if applicable), the outcome of event, and date of resolution (if applicable).

An increase in the severity of a previously reported AESI or SAE during the trial will be reported as a new AESI or SAE with higher severity. A decrease in the severity of a previously reported AESI or SAE during the trial, will not require changes to the reported severity. Worsening of a condition, recurrent episodes, and further complications if any are to be reported as a follow-up of the original event.

All SAEs will be reported by the site staff to the sponsor via the eCRF within 24-hours of first becoming aware

of the event. Additional information will be collected including, seriousness criteria, hospitalization date and discharge (if applicable), and procedures performed (if applicable).

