20.5. Appendix 5: Prohibited Drugs During the Trial

Participants receiving the following drugs are not eligible for participation in the trial, and these drugs should not be initiated during the trial unless clinically essential and treatment cannot be provided with add-on medication as mentioned in Section 8.6, page 22. Past use does not contraindicate eligibility, but any prohibited drug should be ceased at or before the Screening visit and a period of at least 2 weeks or 5 half-lives (whichever is longer) must elapse between permanent drug cessation and randomization.

1. Antihypertensive drugs
 - 1.1. Non-trial angiotensin receptor blockers
 - 1.2. Non-trial calcium channel blocker
 - 1.3. Non-trial diuretics of all types, including thiazide, thiazide-like, loop and potassium sparing diuretics
 - 1.4. Alpha-adrenergic blockers
 - 1.5. Angiotensin-converting enzyme inhibitors
 - 1.6. Beta-adrenergic blockers
 - 1.7. Central alpha-agonists
 - 1.8. Renin-inhibitors
 - 1.9. Reserpine
 - 1.10. Vasodilators
2. Endothelin receptor antagonists
3. Nephilysin inhibitors
4. Other drugs that may affect BP
 - 4.1. Corticosteroids (e.g. cortisone, hydrocortisone) excluding topical inhaled and intranasal use
 - 4.2. Liquorice
 - 4.3. Erythropoiesis stimulating agents (e.g. epoetin alfa)
 - 4.4. Calcineurin inhibitors (e.g. cyclosporine, tacrolimus)
 - 4.5. Sodium-glucose co-transporter-2 (SGLT2) inhibitors (eg. dapagliflozin, empagliflozin, canagliflozin)
 - 4.6. Psychiatric drugs that affect blood pressure:⁷⁰ venlafaxine, bupropion, tricyclics, monoamine oxidase inhibitors (MAOis)
 - 4.7. Cocaine, amphetamines or other stimulants, including the appetite suppressant phentermine
 - 4.8. Pseudoephedrine, phenylephrine or other nasal decongestants, excluding topical and intermittent use
 - 4.9. Yohimbine
 - 4.10. Vascular endothelial growth factor pathway inhibitors (e.g. bevacizumab, SORafenib)
5. Intermittent use of phosphodiesterase (PDE) inhibitors (eg sildafenil) do not constitute a contraindication

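### Symptomatic hypotension that starts in the GMRx2 run-in and continues unchanged after randomization is left out of the Week 6 and Week 12 percentages

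*SAP*

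**What the plan says.** SAP 2.4.2.2 lists as a secondary safety outcome "Percentage of participants with symptomatic hypotension from randomization to follow-up Week 12", with a matching outcome to Week 6. Protocol 17.1.2 makes symptomatic hypotension an adverse event of special interest (AESI), so the AESI counting rules in SAP 3.11.1.2 apply. Neither document gives these percentages a derivation of their own.

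SAP 3.11.1.2 does four things:
- It assigns each event to a period and treatment by its start date.
- For events that straddle randomization: "If an AE is ongoing at the time of randomization, it will be allocated to the Period 1 treatment".
- It moves worsening after randomization to Period 2.
- For each period, "any AESI or SAEs that emerges or worsens during the period of interest will be summarized".

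Protocol 17.2.3 governs how sites record repeat events. An increase in severity "will be reported as a new AESI or SAE with higher severity". Otherwise: "Worsening of a condition, recurrent episodes, and further complications if any are to be reported as a follow-up of the original event". The SAP does not mention recurrence.

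Before randomization all participants "enter a single-blind active run-in period for 4 weeks with GMRx2 dose version 2" (Protocol 8.4.1). One criterion for randomization is "Tolerated run-in medication" (Protocol 8.2.1), with no symptom threshold stated.

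**The concern.** Allocating an ongoing event to the earlier period is the usual treatment-emergent convention. It works well when that period is untreated or is common background. Here the earlier period is four weeks on the test product. At randomization the GMRx2 arm continues the same drug, while each dual arm drops telmisartan, amlodipine or indapamide. Whether a dizzy participant stays dizzy is then partly an effect of the randomized treatment.

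The planned count sends that information to Period 1, where everyone took GMRx2 and no comparison with a dual is possible. Protocol 5.7 itself expects that dizziness and hypotension may be increased with GMRx2. If persistence is more common on GMRx2, the omission makes the reported difference too small, in the test product's favour. If it is equal, the difference is right and each arm's percentage is too low for what its label says.

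**Working it through.** **Tracing the rule.** There is no figure in the plan to reproduce, so the first check is to follow each kind of run-in episode through Protocol 17.2.3 and SAP 3.11.1.2.

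| Run-in episode, after randomization | How recorded | In the post-randomization percentage? |
|---|---|---|
| Continues, same severity | Original record, run-in start date | No |
| Continues or returns, more severe | New AESI | Yes |
| Resolved, returns at same severity | Follow-up of original event | Not specified |
| No run-in episode; first episode on randomized drug | New AESI | Yes |

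The first row follows directly from the text. The third does not. An episode that resolved is not ongoing at randomization, so its return could be read as emerging. But a follow-up entry may carry only the run-in start date, and the event fields listed in Protocol 17.2.3 include onset and resolution dates but no recurrence date.

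**Size.** All rates below are assumptions. Let r be the share of randomized participants with a run-in episode. Let a (GMRx2) and b (dual) be the shares of those whose episode continues beyond 14 days at the same severity, or recurs uncounted. Then:
- uncounted percentage = r × a on GMRx2 and r × b on a dual;
- shortfall in the risk difference = r × (a − b).

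The nearest figure for r is the 5.2% with dizziness, presyncope or syncope on a triple pill in the trial with a 6-month outcome (Protocol 5.4). Spread evenly over 26 weeks, 5.2% × 4/26 = 0.8%. As an upper value I take half of it, 5.2%/2 = 2.6%. I set b = a/2.

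| r | a | b | Uncounted, GMRx2 | Uncounted, dual | Shortfall (points) |
|---|---|---|---|---|---|
| 0.8% | 30% | 15% | 0.24% | 0.12% | 0.12 |
| 2.0% | 50% | 25% | 1.0% (6 of 600) | 0.5% (1.5 of 300) | 0.50 |
| 2.6% | 70% | 35% | 1.82% | 0.91% | 0.91 |

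With a = b the shortfall is 0, and each percentage is low by 0.24 (0.8% × 30%) to 1.82 points (2.6% × 70%). A much higher run-in share would give more: r = 5%, a = 80%, b = 40% gives 5% × 40% = 2.0 points. But 5% is about six times the pro-rata 0.8%.

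**Effect on the reported interval.** The counts here are invented, on the planned arm sizes, with the SAP's continuity-corrected Newcombe method:
- counted only, 18/600 vs 6/300: 1.00 points (95% CI −1.77 to 3.15);
- adding 6 and 1, 24/600 vs 7/300: 1.67 (−1.29 to 4.04);
- adding 6 and 2, 24/600 vs 8/300: 1.33 (−1.71 to 3.77).

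The estimate moves and the reading of the interval does not.

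**Carry-over window.** Half-lives are from Protocol 5.6. Five half-lives are:
- amlodipine (30–50 h): 150–250 h = 6.3–10.4 days;
- telmisartan (about 24 h): 5.0 days;
- indapamide (16–18 h): 3.3–3.8 days.

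At 14 days (336 h) at most 0.5^(336/50) = 0.95% of the amlodipine remains. At 3 days (72 h) it is 0.5^(72/30) = 19% to 0.5^(72/50) = 37%, so a short window would charge residual GMRx2 to the telmisartan/indapamide arm.

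**The case against.** The strongest reply is that this is a standard convention and nothing is hidden. Run-in events are tabulated under Period 1 with GMRx2 as the treatment, so they are charged to the test product. More severe episodes are counted, and the forced dose doubling at Week 6 is where worsening is most likely. Symptoms bad enough to stop treatment after randomization should appear in the primary safety outcome, discontinuation due to an adverse event. Orthostatic hypotension is measured at Weeks 6 and 12 whatever the symptom history. Participants must have tolerated run-in and had home SBP of at least 110 mmHg, and investigators could exclude for low clinic BP. What is left is mainly mild, stable symptoms.

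All of this stands, and it keeps the problem small. It does not restore the missing comparison: none of these outputs shows whether run-in hypotension persisted more often on GMRx2 than on a dual.

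The size also has a thin basis. The 5.2% comes from an open-label trial of a different triple pill, and the assumed halving of persistence on a dual creates the whole shortfall. That stands too, and is why the size is given only as a range.

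A reader might infer that recurrent episodes are definitely excluded. The documents do not support that. The SAP is silent on recurrence, and a returning episode could be read as one that emerges. The protocol sentence that files recurrences as follow-up also lists worsening, which the SAP does count, so being filed as follow-up does not by itself mean being left out.

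**Conclusion.** The point holds for episodes that continue at the same severity: SAP 3.11.1.2 leaves them out of the Week 6 and Week 12 percentages for symptomatic hypotension. For same-severity recurrences the supported statement is that the handling is unspecified, so they may be missed.

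The direction depends on persistence. The risk difference is understated only if persistence is more common on GMRx2; with equal persistence only the percentages are low. The effect is probably under 1 percentage point (0.1 to 0.9 with persistence on a dual half that on GMRx2), and this rests entirely on the assumed run-in share and persistence rates. A reader might infer that the trial's tolerability conclusion is at risk. Nothing in the documents shows that: this is one secondary safety outcome, and the illustrative intervals include zero with and without the added cases. It is a modest improvement to consider, with medium confidence.

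**What to change.** In SAP 3.11.1.2, keep the planned count of emergent or worsened events and add the following, fixed before unblinding:

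1. A supplementary per-participant count of symptomatic hypotension to Week 6 and to Week 12. Besides the planned events, it includes any run-in episode still ongoing more than 14 days after the first randomized dose, taken from onset and resolution dates. Run-in episodes that clear within 14 days and do not recur stay in Period 1.
2. A rule for recurrence. An episode that resolved and returns more than 14 days after the first randomized dose counts as emerging in the period in which it returns, where the recurrence date is recorded. Recurrences within 14 days are listed separately, because residual run-in GMRx2 may explain them.
3. n (%) and the Newcombe risk difference with 95% CI against each dual.

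The 14 days exceed five amlodipine half-lives. They also agree with the protocol's wash-out rule in Appendix 5, "a period of at least 2 weeks or 5 half-lives (whichever is longer) must elapse between permanent drug cessation and randomization"; that rule was written for prohibited drugs and is used here only by analogy.

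The cost is one derived variable, one supplementary row set and a blinded check of dates for events that began in run-in. The persistence count uses dates already collected. Recurrences can be counted only where the follow-up entry carries a date, so that part may be incomplete.
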